Potential problems/alternative approaches: Despite our previous experience in collecting 24-hour BP and urinary data, it is possible that some attempts could be incomplete. If this occurs, the dietary intervention would be continued for an additional 24 hours to repeat the measurement. If despite these efforts, one or both of the 24-hour BP or urine collection are unacceptable in an individual, we would assign the salt-sensitive phenotype if clinic-measured mean BP is >5 mmHg higher following the control diet vs. the DASH/SRD segment; this threshold has been previously used to define salt-sensitivity in metabolic syndrome (Chen et al. 2009). This could affect the distribution of salt-sensitivity slightly, but we expect that few patients will have incomplete data and there will be no bias in missing data by underlying phenotype. The detectable effect size would increase based on the degree of imbalance between the number of subjects defined as salt-sensitive vs salt-resistant. In the event that this imbalance is as high as 70%:30%, the detectable effect size with >80% power would be 0.62 with a two-sided Type I error of 5%. If the distribution of salt-sensitivity is markedly different than expected, we would perform a secondary analysis using the median value or other appropriate cutpoint of the quantitative Sodium Sensitivity Index (Castiglioni et al. 2011).

We do not expect substantial difficulty in obtaining cardiovascular measures; [name] is evaluating all proposed echocardiographic parameters in four ongoing studies, including two NIH-funded studies using DASH/SRD as the intervention. A major focus of [name] NIH/NHLBI K23 award has been non-invasive vascular assessment. In the event that one or more of the cardiovascular measures cannot be obtained, multiple imputation methods will be used. In the course of studies conducted by [name] team, >120 subjects have completed dietary interventions, involving provided food and/or dietary counseling, lasting three weeks to four months. Adherence to provided meals has been excellent overall, but it is likely that some non-adherence will occur. The primary analysis will be intent-to-treat; if any subjects are severely nonadherent (via 24-hour urinary sodium or food diary review) we would do secondary analyses excluding these participants.

Study Phase 2: Assess the efficacy of motivational interviewing plus the WHEELS-I program vs. motivational interviewing alone in promoting adoption of the DASH/SRD. Determine the effects of DASH/SRD adoption over a 6-month period on structural cardiovascular HFpEF risk factors in salt sensitive vs. salt-resistant veterans.

*Introduction:* Structural correlates of HFpEF include left ventricular hypertrophy, which strongly predicts HF onset in older adults, left atrial enlargement, which reflects chronically elevated ventricular filling pressures, and stiff central arteries. No previous studies in participants with HTN and metabolic syndrome have examined the relationship between the salt-sensitive phenotype and these HFpEF risk factors after long-term dietary

modification. Current guidelines recommend the DASH/SRD to prevent cardiovascular disease in hypertensives with metabolic syndrome, but adherence to this dietary pattern is declining nationwide. Our working hypotheses are that: 1) When compared to motivational interviewing alone, the addition of the Women's and Men's Hypertension Experiences and Emerging Lifestyles Intervention (WHEELS-I) program, an electronically-delivered tailored messaging intervention, will improve adoption of the DASH/SRD over a six month period, and 2) sustained adoption of the DASH/SRD over 6 months will produce greater improvement in structural cardiovascular HFpEF risk factors in salt-sensitive than salt-resistant subjects, with measures including left ventricular mass index (LVMI, primary outcome), left atrial volume index (LAVI), cfPWV, and BP.

**Phase 2 study design:** We will test our working hypotheses by providing motivational interviewing-based counseling to all participants and randomizing half to the WHEELS-I program, with both interventions described further below. The primary outcome of Aim 2 of this proposal, to be tested in Phase 2 of the protocol, is the intra- and inter-group mean change in DASH/SRD concordance score (Mellen et al. 2008) from the baseline value obtained at the beginning of the study. This score provides 1 point for fully meeting each of 9 DASH/SRD targets and 0.5 for meeting an intermediate level of each target (e.g. fiber 14.8 g and 9.5g/1000 kcal, respectively). The secondary dietary outcome is the group change in mean 24-hour urinary sodium excretion compared to baseline values. Other outcomes of interest are urinary potassium, microalbuminuria, and the nutrient composition from three day food diaries.

We will also test if DASH/SRD adoption differentially improves HFpEF-associated structural cardiovascular parameters in salt-sensitive vs. salt-resistant subjects (as they were defined by BP response in *Phase 1*). The primary cardiovascular outcome of *Phase 2* is the change from baseline (Week 2 visit) to 6 months in left ventricular mass index (LVMI, indexed to height2.7). This measure was chosen because LVMI is a strong risk factor for incident HF (Gottdiener et al. 2000), can decrease after 6 months of dietitian-counseled sodium restriction (Jula et al. 1994, Liebson et al. 1995), and is relevant to the pathophysiology of HFpEF (Melenovsky et al. 2007). Key secondary outcomes include cfPWV (see *Aim 1*), left atrial volume, indexed for body surface area (LAVI) (Melenovsky et al. 2015), and 24-hour mean BP.

Phase 2 data collection: History and exam, questionnaires, blood tests, 24-hour BP and urine collections will be performed at months 1 and 6 of Phase 2 (see Study procedures above). Dietary concordance with DASH/SRD, the measure of exposure in Phase 2, will be assessed via Block Food Frequency Questionnaire and 24-hour urine sodium excretion at month 6, and 3-day food diaries immediately prior to the Month 1 and Month 6 visits. Arterial tonometry, echocardiography, SDF microscopy, and the mini-SBT will be performed at Month 6 of Phase 2 (see also Figures 7 and 8). Following Phase 2, participants will have follow-up after 6 months via telephone interview to assess cardiovascular events and vital status; subjects will be mailed a Food Frequency Questionnaire to evaluate persistence of dietary patterns after study participation; and there may be an optional in-person visit determined by study staff, based on need, for an additional arterial tonometry procedure and blood pressure check.

Dietary intervention: Phase 2 of the protocol will begin within 2 weeks of the end of Phase 1, and typically will begin immediately (i.e., as part of the week 4 visit). During this period, participants will be placed back on their prior antihypertensive therapy, if any, under [name] guidance. Prior to the first Phase 2 visit, subjects will be randomized to control (motivational interviewing only) or the addition of the WHEELS-I program. At the first visit of Phase 2, participants will update their cognitive representation of the DASH/SRD, and have an inperson dietitian session during which motivational interviewing techniques will be employed to explore and support willingness to change dietary habits. If the participant desires, the motivational interviewing portion of the visit may be conducted by telephone. Motivational interviewing-based counseling will continue via telephone during week 2, month1 visit, and at months 2 and 4.

The WHEELS-I program consists of three daily activities: in the morning, reading messages that reinforce the key DASH/SRD diet educational components (e.g., types of foods, number of servings, rationale for recommendations) related to a specific dietary goal, then brief journaling of emotions and thoughts related to this goal; in the evening, record of DASH/SRD adherence during that day. An example: goal, eat 4-5 servings of fruits and vegetables per day; messages, try fresh fruits in season, make a fruit salad of "light" or "natural juice" canned fruits, keep dried fruits in your desk or car for snacks; journaling, "I am learning to appreciate the

sweetness of fruit." The daily activities are designed to take less than five minutes. Participants assigned to the WHEELS-I program may choose whether to receive messages via email, in identical fashion to the study shown in the *Preliminary Data* above, or via a newly created smartphone mobile application. Both methods will link to the same web-based information and surveys, which will collect data and store it under subject number in the Amazon.gov cloud storage system, where data will be accessible only by study personnel.

For the first 30 days of *Phase 2*, WHEELS-I participants will receive a structured series of messages that cycle through the DASH/SRD goal areas, e.g. increasing consumption of fruits and vegetables, whole grains, nuts and legumes, and low-fat dairy and reducing intake of sodium, red meat, and sweets. At the Month 1 dietitian visit, all participants will again update their DASH/SRD cognitive representation. Those assigned to WHEELS-I will then decide how frequently to receive morning messages for the next 30 days (evening messages will continue for the next 60 days). Options will include 1) continue daily morning messages, 2) morning messages three times a week, 3) morning messages once a week.

These ongoing messages will be tailored toward challenges identified through motivational interviewing sessions and updating of the DASH/SRD cognitive representation. Message tailoring is a process that includes 1) assessment of individual characteristics relevant to a particular behavior, 2) algorithms that use assessment data to generate intervention messages that address the needs of each user and 3) individual feedback that delivers these messages in a clear and vivid format. Messages will be tailored using the Michigan Tailoring System, an open-source platform developed by the Center for Health Communication Research.

Throughout the first 90 days, if there are less than 3 logins weekly for evening messages noted after 2 consecutive weeks, a message will be sent to inquire how the participant is doing and elicit any problems. At 90, 120, and 150 days, all subjects will be provided the option to continue messages for an additional 30 days. Training for dietitians to facilitate WHEELS-I will be performed by [name], the program's creator. As recommended by the NIH Behavior Change Consortium (Bellg et al. 2004), training will be standardized, delivered by a single trainer, and reinforced (every 6 months). Skill acquisition will be confirmed at baseline and retention by facilitating dietitians observed regularly (e.g., every 10 subjects entering *Phase 2*) by [name]. Receipt of treatment by participants will be assessed via the proportion of messages accessed and responded to. At the end of 16 weeks, all app users will be sent a secure WHEELS-I feedback survey through REDCap, via email. All responses will be automatically uploaded and stored in the secure REDCap application.

The mobile WHEELS application will be downloadable for either iOS or Android from the Apple or Google Play stores, respectively. The participant will receive a unique code to unlock the WHEELS-I application for download. The application will include an overview of DASH/SRD principles, daily notifications and reminders to both influence and measure adherence to the DASH/SRD as above, and positive encouragement for meeting goals. The system will provide a web-based management dashboard for the research team that allows for data collection from the mobile app or email replies, extracts and analysis by the researchers, and adherence to VA security requirements through the use of Amazon.gov cloud hosting.

Sample size and power: The sample size for *Phase 2* is set by the goals of *Aim 1* and influenced by drop-out during the 6 months of the interventions to promote DASH/SRD adoption. We assume that an additional 10% of subjects will drop out during *Phase 2* and that the dropout rate will be equal in salt-sensitive and salt-resistant participants, resulting in 90 subjects with evaluable data. The primary outcome of *Aim 2* of this proposal is the DASH/SRD concordance score from the Block Food Frequency Questionnaire in participants assigned to the WHEELS-I group vs. motivational interviewing alone. Based on national survey data and our preliminary work, we expect the mean baseline (Week 2 visit) dietary score to be 2.5±1.5. A sample size of 90 provides >80% power to detect an intra-group change of 0.6 between baseline and the end of study, based on paired t-testing two-sided Type I error of 5%. This sample size provides >80% power to detect a differential between group change in dietary score of 0.9, based on a two-sample t test and two-sided Type I error of 5%.

With regard to cardiovascular parameters, a sample size of 90 provides >80% power to detect an effect size of 0.6 in the primary endpoint of change from baseline to month 6 in LVMI between salt-sensitive vs. salt-resistant subjects (assuming a 50:50 split of salt sensitive vs. salt-resistant participants), with a two-sided Type I error of

5%. This between-groups comparison is based on a two-sample t test. Conservatively assuming that the standard deviation of the change in LVMI between baseline and 6 months ranges between 4 to 7 g/m2.7 (Blumenthal et al. 2010), this effect size translates to mean group differences of 2.4 to 4.2 g/m2.7. This would represent a 5-10% decrease in LVMI from baseline in salt-sensitive subjects (vs. no change in salt-resistant), similar to that in previous studies of dietary sodium restriction (Jula et al. 1994, Liebson et al. 1995).

Analysis plan: Paired and 2-sample t-testing will be used to analyze changes in DASH/SRD concordance score as above, as well as changes in 24-hour urinary sodium excretion. The methods to analyze cardiovascular changes in *Aim 2* will be identical to those used in the comparison of salt sensitivity phenotypes in *Aim 1* (see above). Important covariates in the models to compare changes in cardiovascular parameters by salt-sensitive/resistant phenotype will be the degree of DASH/SRD concordance and changes in 24-hour BP.

Potential problems/alternative approaches: While motivational interviewing and the WHEELS-I program have been effective in our preliminary studies, we expect individual variance in DASH/SRD adoption. The primary analysis will be an intent-to-treat framework; secondary analyses will test interaction with the level of DASH/SRD adoption. (Mellen et al. 2008) We expect that participants who successfully adopt DASH/SRD will substantially change their eating habits. The WHEELS-I program does not target weight loss, but since sodium intake correlates with caloric intake (Guenther et al. 2013) it is possible that some veterans may lose weight during *Phase 2*. We do not a *priori* expect differential weight loss in salt-sensitive and salt-resistant subjects. However, since cfPWV and LVMI can both be reduced through weight loss, we will perform analyses adjusted for *Phase 2* weight changes (Blumenthal et al. 2010). If the proportions of salt-sensitive and salt-resistant subjects are not equal (say 60%:40%), we would retain >80% power to detect effect size of 0.61.

Specific Aim 3 (spans Study Phases 1 and 2): Determine effects of DASH/SRD feeding and longer-term adoption on microvascular function, and assess the relationship between endothelial glycocalyx integrity/sodium buffering and cardiovascular response to DASH/SRD.

Introduction: Small-vessel oxidative stress and inflammation are critical mechanisms of cardiovascular injury in salt-sensitive animals, and recent data strongly implicate microvascular damage in HF pathophysiology. The endothelial glycocalyx (eGC) is a thin network lining the lumen of blood vessels, and if damaged may mediate the mechanisms and vascular consequences of salt-sensitivity. Our working hypothesis is that the DASH/SRD will improve microvascular function in comparison to control diet, and differentially so in salt-sensitive subjects. We will test this hypothesis using sublingual sidestream dark-field (SDF) microscopy. We further hypothesize that poor eGC integrity will identify subjects who have greater cardiovascular improvement with DASH/SRD. This hypothesis will be tested using SDF microscopy and a novel "mini-Salt Blood Test" (see Background and Significance above for description of these procedures).

Aim 3 analysis plan: To determine the effects of the DASH/SRD intervention and adoption on microvascular parameters and the differential impact of salt-sensitivity, we will use the approaches described in Aims 1 and 2 for microvascular density and RBC filling % (measures of microvascular structure and function). To assess the relationship between eGC and salt-sensitivity, we will characterize the relationship between mean baseline PBR and mean baseline ESS (measures of eGC thickness and sodium-buffering capacity) and the salt-sensitive phenotype (as defined in Aim 1). We will also assess the relationship of these parameters with cardiovascular functional and structural measures described in Aims 1 and 2. For example, we will test whether mean baseline ESS differs by salt-sensitivity phenotype using a two-sample t-test or simple linear regression (to include adjustment for important covariates). Model performance measures will be used to assess the discrimination of PBR and ESS (vs. salt-sensitivity) for changes in cardiovascular function and structure [e.g., area under the receiver-operating-characteristic curve, net reclassification, and integrated discrimination improvement (Pencina et al. 2008)]. Descriptive analyses of baseline and changes in microvascular and cardiovascular function and structure will use graphical and summary statistics.

Potential problems/alternative approaches: Technical factors could prevent SDF microscopy acquisition in a few participants. If this occurs, subjects will still have all other cardiovascular measures as well as glycocalyx assessment with the mini-SBT. We have successfully obtained the mini-SBT in over 200 participants. In the rare event of a technical failure, we would simply repeat the test. Despite supportive data as above, it is

possible that the mini-SBT results will not predict BP changes during DASH/SRD. Given the mechanistic links between eGC function and sodium-induced vascular damage (*Figure 2*), it is also possible that the mini-SBT is more effective than BP changes in identifying subjects with beneficial cardiovascular effects during DASH/SRD.

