#### D. APPROACH

General Design: This 7-month dietary intervention study will recruit from the Ann Arbor Veterans Affairs Health System and affiliated Community-Based Outpatient Clinics (CBOCs). We hypothesize that dietary modification with the DASH/SRD will improve HF-associated cardiovascular dysfunction in veterans with HTN and metabolic syndrome, and that differential improvements will occur in those with a salt-sensitive BP phenotype vs. those with salt-resistant BP. The study will take place in two phases (Figure 7): Phase 1 participants will consume their usual diet, followed by a DASH/SRD for 14 days each. Salt-sensitive vs. salt-resistant status will be defined by 24-hour BP measurement at the end of each segment In Phase 2, all participants will receive motivational interviewing-based dietary counseling; half will participate in WHEELS-I to promote DASH/SRD adoption over 6 months.

Participants will have a clinical evaluation at 4 time points (denoted by ↑ in *Figure 7* and described below): at weeks 2 and 4 of the *Phase 1* crossover intervention, and at 1 and 6 months of the *Phase 2* DASH/SRD adoption period.

The *Phase 1* primary analysis will evaluate cardiovascular functional changes during usual diet and DASH/SRD diet periods, and test for interaction with saltsensitivity status. Phase 2 will assess the performance of WHEELS-I in promoting DASH/SRD adoption, and evaluate cardiac structural changes between salt-sensitive and salt-resistant

Figure 7: Overall study timeline

Abbreviations: DASH/SRD, sodium-restricted Dietary Approaches to Stop Hypertension; SR, salt-resistant; SS, salt-sensitive; WHEELS-I, Womens' and Men's Hypertension Experiences and Emerging Lifestyles Intervention; **†** = Clinical visit (see text)

participants (as they were defined by BP measurement in *Phase 1*). After completion of *Phase 2*, telephone clinical and mailed dietary questionnaire follow-up will occur after 6 months. An optional, in-person visit may also be performed at this time to obtain arterial tonometry data and clinic blood pressure.

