- Safety Monitoring: Patients will perform home BP monitoring with their own personal cuff or a provided Omron 7 series automated cuff (Omron Healthcare, Lake Forest, IL). Monitoring will be daily during the run-in period and *Phase 1* of the study, and at least weekly thereafter if systolic BP is >180 or <100 mmHg on more than one occasion, or if symptoms suggest hyper- or hypovolemia (e.g., worsening/new edema, dizziness), the participant will be scheduled for an in-person safety visit. Targeted history and physical will be performed by a clinician-investigator, with laboratory or other testing obtained based on the clinical presentation. Antihypertensive medications may be adjusted at this visit if needed for participant safety. Safety visits may also be scheduled for worsening glycemic control in diabetic participants. See *Human Subjects Protection* section for additional details.

Study phase 1: Phenotype veterans with HTN and metabolic syndrome as salt-sensitive or salt-resistant; determine effects of a 2-week DASH/SRD intervention vs. control diet on HFpEF functional cardiovascular risk factors in salt sensitive compared to salt-resistant veterans.

Introduction: Animal models, cohort studies, and our preliminary work suggest that the DASH/SRD would favorably affect cardiovascular parameters that predict incident HFpEF in veterans with HTN and metabolic syndrome, and have a stronger effect in salt-sensitive individuals. Our working hypothesis is that the DASH/SRD will produce significantly greater improvement than control diet in HFpEF risk factors including large-arterial stiffness (carotid-femoral pulse wave velocity [cfPWV], primary outcome), left ventricular diastolic function, and left ventricular systolic function. We further hypothesize that the improvement in these measures will be greater in salt-sensitive veterans. We will test our hypotheses in a 2-sequence, 2-period, 2-treatment comparison of DASH/SRD vs. control diet.

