**Phase 1 study design:** Consented participants will have clinic BP measured at the screening visit and will enter a two-week usual diet period, during which antihypertensive medications, with the exception of calcium channel blockers, will be weaned off under [name] supervision and with guidance from daily home BP monitoring. During this time period, the participant will consume their usual diet. Potential subjects with ontreatment, resting, average systolic BP of > 160 mmHg at the screening visit will be excluded from further

participation, as will those with symptomatic hypertension or systolic BP of > 180 mmHg on more than one occasion during the ad-lib dietary period.

Following the usual diet period and the week 2 visit, participants will consume the DASH/SRD diet for 14 days each. This time period is sufficient to demonstrate changes in BP and arterial stiffness, which peak at 2 weeks after dietary sodium modification (Gates et al. 2004). In addition to in-clinic BP measurement, 24-hour ambulatory BP will be obtained at the end of each dietary sequence. We expect that the DASH/SRD will reduce BP across the cohort, but differentially on an individual basis (Sacks et al. 2001).

The salt-sensitive vs. salt-resistant phenotype will be defined as a change in 24-hour mean BP of ≥8 mmHg between control and DASH/SRD dietary segments (Castiglioni et al. 2011). Based on previous studies in patients with HTN, we expect that 30-50% of participants will be classified as salt-sensitive (Elijovich et al. 2016). The 24-hour ambulatory BP monitoring and 24-hour urinary collections will be used to provide an alternate definition of salt-sensitivity. Specifically, the quantitative Sodium Sensitivity Index will be calculated as the change in 24-hour mean BP divided by the change in 24-hour urinary sodium excretion between DASH/SRD and control diet periods (Castiglioni et al. 2011).

The *Phase 1* primary outcome is the cfPWV compared at the end of usual diet and DASH/SRD. This parameter was chosen because of its association with incident HF in community-dwelling elderly (Tsao et al. 2015) and its high sensitivity and specificity for HF in older adults with unexplained exertional dyspnea (Weber et al. 2013). Key secondary outcomes include ventricular diastolic function (k; ventricular stiffness) and systolic function (global longitudinal ventricular strain) and left atrial reservoir function (left atrial strain).

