Sample size and power: The sample size is based on a combination of logistical considerations and power required to detect important differences in the primary endpoint of change in cfPWV in the context of a randomized crossover design. Sample size is based on a 2-sequence, 2-period, 2-treatment crossover design for continuous endpoints (using paired t test for mean differences). We conservatively assume a within-subject correlation of 0.70 for cfPWV measurements, based on our DASH-DHF pilot (0.81) and literature showing same-day correlation >0.90 (Wimmer et al. 2007) using the Sphygmocor device. We also assume approximate 10% dropout rate during Phase 1 of our study. Under these assumptions and using a two-sided type I error rate of 5%, 100 subjects, 50 allocated to the DASH/SRD-control diet sequence and 50 allocated to the control-DASH/SRD diet sequence, provides >80% power to detect an effect size (mean treatment difference/standard deviation) of 0.22 and >90% power to detect an effect size of 0.26. For comparison purposes, the effect size of cfPWV changes with DASH/SRD in our preliminary work in HFpEF has been 0.4-0.6; in dietary sodium restriction studies in healthier populations than we plan to study, the effect size is at least 0.2-0.4 (Seals et al. 2001, Todd et al. 2010). This sample size provides >80% power to detect an effect size of 0.5 in cfPWV change between salt-sensitive vs. salt-resistant subjects. This is a between-groups comparison based on a two-sample t test and two-sided Type I error of 5%.

Analysis plan: We will examine the distributions of outcomes under each treatment (e.g., DASH/SRD and control diet), as well as by salt-sensitive phenotype. Graphical approaches such as boxplots and scatterplots will be used, allowing identification of outliers, linearity, and correlation of measurements within subject and across time. If the distributional assumptions of our models are not met, transformations will be employed.

Obvious outliers unrelated to data entry error will prompt reconfirmation of acquisition methods and quality by another blinded investigator. We expect no carryover effects due to the two week duration of each dietary segment, a sufficient interval to match sodium intake and excretion even in subjects with chronic kidney disease (McMahon et al. 2013), who have more difficulty achieving this balance.

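### Phase 1 is specified and powered as a randomised two-sequence diet crossover but given in one fixed order, so diet cannot be separated from time, and the SAP states no whole-cohort test of diet

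*Protocol*

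**What the plan says.** **As a crossover.** The Introduction to Study phase 1 in the protocol says the hypotheses will be tested "in a 2-sequence, 2-period, 2-treatment comparison of DASH/SRD vs. control diet". The leading hypothesis is that "the DASH/SRD will produce significantly greater improvement than control diet in HFpEF risk factors including large-arterial stiffness", with cfPWV as primary outcome. Sample size and power calls the design a randomised crossover, with "50 allocated to the DASH/SRD-control diet sequence and 50 allocated to the control-DASH/SRD diet sequence". The Phase 1 Analysis plan specifies a linear mixed model on all randomised participants, with fixed effects for sequence, period and diet and adjustment for baseline cfPWV.

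**As a single order.** General Design says that "participants will consume their usual diet, followed by a DASH/SRD for 14 days each", and that the Phase 1 "primary analysis will evaluate cardiovascular functional changes during usual diet and DASH/SRD diet periods". Phase 1 study design agrees on the order: "Following the usual diet period and the week 2 visit, participants will consume the DASH/SRD diet for 14 days each". In the Phase 1 Dietary intervention section, the provided meals start after the Week 2 visit. The only treatment randomisation described is to WHEELS-I, before the first Phase 2 visit. The random blocks of 10 in Recruitment strategy order the invitation letters, not the diets.

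**SAP.** The Statistical Plan gives the same single order and states that Phase 1 came before randomisation. Its Phase 1 comparison is salt-sensitive versus non-salt-sensitive, by linear regression adjusted for the baseline value. It then restates the 50/50 two-sequence basis and the 0.22 and 0.26 effect sizes.

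**The concern.** In a two-order crossover, a change over time that is common to everyone is removed by the period term. In one order it is added to the diet estimate. The Phase 1 mixed model therefore cannot deliver the diet effect it names. Software that drops aliased terms would return the Week 4 minus Week 2 change under the label of diet.

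The documents name one candidate time effect. During the usual-diet period "antihypertensive medications, with the exception of calcium channel blockers, will be weaned off", and the protocol does not say how long before the Week 2 visit this is complete.

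The adjustment for baseline cfPWV has a related fault. Figure 8 shows no arterial tonometry before Week 2, so the only available baseline is also the usual-diet outcome.

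The diet comparison of cfPWV is the Phase 1 working hypothesis and primary outcome. A reader following the protocol would report an uncontrolled change as a randomised effect. A reader following the SAP finds no test of it.

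**Working it through.** **Inputs** (Phase 1 Sample size and power, repeated in the SAP): n = 100, within-subject correlation 0.70, two-sided 5%, paired t test, effect sizes 0.22 and 0.26 as mean difference over SD.

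**1. The plan's power.**
SD of the paired difference = √(2 × (1 − 0.70)) = 0.7746 single-visit SD.
Noncentrality = effect size / 0.7746 × √100, on 99 df, critical value 1.984.
- 0.22: noncentrality 2.84, power 80.3%.
- 0.26: noncentrality 3.36, power 91.4%.

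The stated >80% and >90% reproduce. A paired Week 4 versus Week 2 test with one order has the same power; what changes is what the difference means.

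**2. Estimability.** Take the columns intercept, sequence, period and diet for 100 participants by 2 periods.
- Two orders, 50 each: rank 4 of 4.
- One order: sequence is constant and so aliased with the intercept, and period equals diet in every row. Rank 2 of 4.

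No increase in n repairs this.

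**3. What an assumed time effect would do.** The documents give neither size nor direction, so these shifts are assumptions, in single-visit SD units. The formula is that of step 1.

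*No diet effect, time shift only:*

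| Shift (SD) | Noncentrality | Declared significant |
|---|---|---|
| 0.05 | 0.65 | 9.8% |
| 0.10 | 1.29 | 24.8% |

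The nominal rate is 5%.

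*True benefit of 0.22 SD, time shift in the opposite direction:*

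| Shift (SD) | Net change (SD) | Noncentrality | Power |
|---|---|---|---|
| 0.05 | 0.22 − 0.05 = 0.17 | 2.19 | about 58% |
| 0.10 | 0.22 − 0.10 = 0.12 | 1.55 | about 34% |

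For scale, the cfPWV SDs in the protocol's HF pilot are 2.2 and 3.0 m/s. A shift of 0.05 SD is then 0.11 to 0.15 m/s, and 0.10 SD is 0.22 to 0.30 m/s.

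**4. Where the diet comparison is analysed.**

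| | Protocol | SAP |
|---|---|---|
| Order of diets | Two orders (Introduction, Sample size); one order (General Design, Phase 1 study design, Dietary intervention) | One order; two-sequence basis for n repeated |
| Whole-cohort diet comparison | Mixed model, diet aliased with period | None stated |
| Phenotype comparison | Interaction in the same model | Baseline-adjusted regression |

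**The case against.** The SAP has already moved on. It states the single order, says Phase 1 preceded randomisation, names the phenotype groups as comparators and drops the sequence and period terms. It gives the two-sequence design as the basis on which the sample size was set, which is a proper historical record. A single-order feeding phase is also a legitimate way to phenotype participants. All of this stands. What remains is protocol text that was not updated, no SAP sentence saying that the design departed from the sample-size assumption, and no whole-cohort test.

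Several stronger readings are tempting, and the documents do not support them:
- *The sponsor will report a randomised diet effect.* The SAP does not plan the crossover model. That risk arises only for someone working from the protocol.
- *The power calculation is wrong.* The 0.22 and 0.26 figures are correct arithmetic.
- *Any time effect favours DASH/SRD.* No direction is given. If the effects of withdrawal continued after Week 2 and raised cfPWV (an assumption), they would mask a benefit.
- *Drug changes at safety visits are a further time effect.* The protocol says "Antihypertensive medications may be adjusted at this visit if needed for participant safety". A change made because the diet altered BP would be a consequence of diet, and a randomised crossover would not remove it.
- *The salt-sensitivity comparison falls too.* A cfPWV time effect common to both phenotypes cancels between fixed groups. The caution is that phenotype is defined by BP change over the same two visits.

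The separate 0.5 effect size for the phenotype comparison is a different question, and nothing here rests on it.

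**Conclusion.** The point holds as an inconsistency that must be resolved. The protocol describes two incompatible Phase 1 designs. Under the single order, which the SAP confirms, its diet effect is aliased with period (rank 2 of 4), and the SAP states no whole-cohort test of the Phase 1 primary outcome.

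The aliasing and the missing test follow from the text and need no assumption. The numerical consequences rest on assumed shifts of 0.05 to 0.10 SD, n = 100 and correlation 0.70. They run in both directions: about 10% to 25% false positives, or a fall in power at 0.22 from 80.3% to about 58% to 34%. They show sensitivity and are not an estimate of bias in this trial.

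**What to change.** **(a) Reconcile the design text.** If one order was used:
- State in the Study phase 1 Introduction, Sample size and power, Analysis plan and SAP that Phase 1 is a single-sequence, non-randomised before-after comparison.
- Keep the record that n was set under a crossover assumption, and say that the 0.22 and 0.26 power applies to the within-person change.
- Correct the remaining crossover wording: the label in General Design, the references to dietary sequences and to 14 days of each diet in Phase 1 study design, and the carryover sentence in the Analysis plan.

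If order was in fact randomised, correct General Design, Phase 1 study design, Dietary intervention and the SAP instead.

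**(b) With one order, state the same diet analysis in both documents.** Test the mean Week 4 minus Week 2 change in cfPWV with the paired t test used for sample size, or the equivalent mixed model with a single diet/visit term. Use no sequence term, separate period term or Week 2 covariate, and keep the protocol's multiple imputation. Label the test as added after data collection. Report it as an uncontrolled before-after change that could be biased either way, and give the number of participants whose antihypertensives changed between Week 2 and Week 4. Medications are already updated at each visit.

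**(c) Keep the SAP's phenotype regression** as a separate effect-modification analysis, noting that phenotype is defined by BP change over the same interval.

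**Cost.** Wording, one test and one count, from data the plan already collects, with no change to n. The price is a weaker causal claim for the Phase 1 diet effect and a post-data label on the added test.
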